**3.4.7 Evaluable patient**

An evaluable participant is defined as one who has received study medication and has provided sufficient data to meet the primary endpoint of determining the presence or absence of a DLT, *and* sufficient data relating to the main secondary outcome measures. Whether sufficient data has been obtained for this purpose will be determined by clinical judgement on an individual participant basis.

In the unlikely event that a participant decided to self-discharge themselves after dosing but prior to the end of the 5 hour evaluation window, this participant could be counted as an evaluable patient with no DLTs provided they had completed the 2-3h timepoint and that this self-discharge had occurred within a clinical picture of stable or normalising observations. Attempts to complete the follow-up phone call would be made to confirm absence of DLT as defined by 'intervention level'.

In the event of an inability to acquire sufficient data, as defined above, the decision on whether to include an individual's data in the primary (DLT) or secondary analysis, or whether that individual would be replaced, would be made on a case by case basis.

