**3.4.6 Evaluation window**

The evaluation window for primary and secondary outcome measures will begin at dosing and end at 5 hours post-dose, with the exception of the 'intervention level' (as defined in the DLT definition) which will begin at dosing and continue until the last follow-up phone call. This call will be conducted the following day, and the window will be extended if the participant is experiencing sedation or other symptoms.

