### **5.4.2 Methadone Dosing**

Participants will take their usual dose of prescribed daily methadone, and the time noted.

NB: In those receiving daily prescription methadone, given their long-term use, plasma levels will be at steady-state during the day. The vast majority of participants take their methadone in the morning, therefore on experimental visits, participants will bring their

usual methadone dose with them to the research facility, and consume it under observation on the premises, shortly after arrival. Maximal plasma levels of methadone are reached in 1.8-3.8h with half-life of ~24hrs (independent of dose, (Wolff et al., 1993). Our previous experience is that a short delay in taking methadone is acceptable to participants and we do not anticipate substantial discomfort. However, to minimise this, the methadone will be taken as early as possible, and the gap between methadone and baclofen administration will be kept short (~40-60 minutes).

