### **5.4.15 Discharge**

Participants will be required to remain under supervision for a period of 5 hours after they receive baclofen/placebo, and remain at the research facility until approved for discharge by the study physician. Staff will ensure that any adverse impacts etc have attenuated before the participant leaves. Study staff will remind participants of relevant study contact details, including a 24-hour mobile telephone number for the on-call study doctor.

Where possible, study staff will arrange for a taxi to take the participant home.

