#### **5.7.1 Baclofen in licensed indication**

For baclofen, BNF recommended maximum dose is 100mg/d for licensed indication of spasticity. Example SmPCs for generic baclofen can be found here:

Accord UK Ltd (10mg tablets)

<https://www.medicines.org.uk/emc/product/5728/smpc>

Advanz Pharma (10mg tablets)

<https://www.medicines.org.uk/emc/product/11781/smpc>

Mylan (10mg tablets)

<https://www.medicines.org.uk/emc/product/2594/smpc>

Baclofen is the only selective GABA-B agonist licensed for human use. Originally developed as a potential anti-epileptic in the 1920s, it was found to have anti-spastic effects and is currently used for the treatment of spastic movement, especially in instances of spinal cord injury, spastic diplegia, multiple sclerosis, and amyotrophic lateral sclerosis. It is an orally active *g*-aminobutyric acid (GABA) derivative, p-

chlorophenyl-gamma aminobutyric acid. Its primary action as an antispasticity agent is via simulation of GABAB-receptors resulting in depression of monosynaptic and polysynaptic reflex transmission. Baclofen increases K+ conductance resulting in postsynaptic inhibition and reduces Ca2+ influx and the release probability of excitatory transmitters (glutamate and aspartate) causing presynaptic inhibition in the brain and spinal cord (Katzung, 2009). Baclofen also exerts an antinociceptive effect and may act at supraspinal sites producing CNS depression. Baclofen may also modulate dopamine release in the mesocorticolimbic system by targeting neurons in the ventral tegmental area (Cruz et al., 2004).

Over its many years of use, baclofen has proven to be a very safe drug with few side effects. The main adverse effects are somnolence, dizziness, muscle weakness, and headache. Baclofen has good absorption after oral administration (75%), with peak serum concentrations achieved in 2–4 h. It is weakly bound (30%) to plasma proteins, and is eliminated primarily via the kidneys, 85% as the unchanged parent compound, with an estimated elimination half-life of 3-4 hours. The therapeutic serum concentration for spasticity is 0.08 to 0.4 microgram/ml.

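### A participant who leaves before the 5-hour DLT window closes can be scored as having no DLT after a loosely defined 2–3 h time point; the bias is probably small but runs only toward under-counting DLTs

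*Combined protocol and SAP*

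**What the plan says.** Section 3.4.6 fixes the window for the primary outcome: it "will begin at dosing and end at 5 hours post-dose". Only the intervention-level criterion runs on to the follow-up call. Section 5.4.15 matches this: "Participants will be required to remain under supervision for a period of 5 hours after they receive baclofen/placebo".

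Section 3.4.7 makes an exception for early self-discharge, which it describes as unlikely: "this participant could be counted as an evaluable patient with no DLTs provided they had completed the 2-3h timepoint", and provided that "this self-discharge had occurred within a clinical picture of stable or normalising observations". On later follow-up it adds: "Attempts to complete the follow-up phone call would be made to confirm absence of DLT as defined by 'intervention level". The same section leaves sufficiency of data to clinical judgement and allows inclusion or replacement to be decided case by case.

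On timing of exposure, Section 5.4.2 states "Maximal plasma levels of methadone are reached in 1.8-3.8h with half-life of ~24hrs", with methadone taken about 40–60 minutes before baclofen. Section 5.7.1 describes baclofen as having "peak serum concentrations achieved in 2–4 h", and the exploratory outcomes in Section 3.4.5 use the same 2–4 h interval. Section 5.4.3 gives about 1–2 h, specifically 88–102 minutes at 60 mg.

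Section 8.3.2 feeds binary DLT data from all earlier cohorts into the model, updates after at most every 3 patients, and permits escalation only if the current cohort has no DLT.

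**The concern.** The endpoint is whether a DLT occurs within 5 hours. A DLT-free record that stops at 2 or 3 hours is incomplete, yet the rule allows it to enter the model as a full negative. Section 8.3.2 describes no status between DLT and no DLT.

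The cut-off is also unclear. The schedule in Section 4.3.2 has sets at 120 and 180 min and nothing called 2–3 h, so the earliest qualifying departure could be read either way.

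The two safeguards do not fill the gap. The condition on observations describes the participant at departure, not the remaining 2–3 hours. The call is only attempted, and for DLT purposes it confirms only intervention level. Section 3.4.2 also defines DLTs by NEWS2, SpO2, respiratory rate, apnoea with desaturation, GCS and QTc, and a next-day call cannot establish these.

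At stake are the escalation decision and the all-safe stop (probability above 92.5% that risk is 25% or below at 90 mg baclofen with 120 mg methadone). A late DLT that goes unseen pushes both in the permissive direction.

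**Working it through.** The plan has no figure of its own to reproduce here. Section 8.1 says no power calculation was done, and the sample-size section mentions simulations without inputs or results. The check is timeline arithmetic plus an illustration.

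**1. What goes unobserved** (schedule in Section 4.3.2; window 300 min)
- Scheduled post-dose NEWS2 and GCS: 60, 120, 180, 240, 300 min. Scheduled post-dose ECG: 120, 300 min.
- Leaving just after 180 min: (300 − 180)/300 = 40% of the window; NEWS2/GCS at 240 and 300 missed, 2 of 5; ECG at 300 missed, 1 of 2.
- Leaving just after 120 min: (300 − 120)/300 = 60%; NEWS2/GCS at 180, 240 and 300 missed, 3 of 5; ECG 1 of 2.

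**2. Methadone peak on the baclofen clock** (Section 5.4.2: 1.8–3.8 h, gap about 40–60 min)
- Gap 60 min: 1.8 − 1.0 = 0.80 h to 3.8 − 1.0 = 2.80 h.
- Gap 40 min: 1.8 − 0.67 = 1.13 h to 3.8 − 0.67 = 3.13 h.
- After a 120 min departure the peak can lie up to 0.80 h (60 min gap) or 1.13 h (40 min gap) ahead. After 180 min it can lie ahead only at the extreme, by 0.13 h (about 8 minutes) with a 40 min gap.

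**3. Baclofen peak**
- On 2–4 h (Sections 3.4.5 and 5.7.1): up to 2 h after a 120 min departure, up to 1 h after a 180 min departure.
- On 88–102 min, that is 1.47–1.70 h (Section 5.4.3): before either departure.

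**4. Size of the under-count** (illustration; f and q are assumed, not in the documents)
- Let p be the true DLT risk, f the share leaving early, and q the share of their DLTs that first appear after departure. Recorded rate = p(1 − fq).
- p = 25%, f = 5%, q = 10%: 0.25 × (1 − 0.005) = 24.9%.
- p = 25%, f = 20%, q = 50%: 0.25 × (1 − 0.10) = 22.5%.

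**5. One early leaver in a cohort of 3, p = 25%**
- Fully observed: P(no DLT) = 0.75³ = 42.2%.
- With one early leaver: 0.75² × [1 − 0.25(1 − q)]. For q = 10%: 0.5625 × 0.775 = 43.6%. For q = 50%: 0.5625 × 0.875 = 49.2%.

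The effect on the 25% and 92.5% stopping thresholds cannot be computed, because the model priors are not in the documents.

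**The case against.** The rule is permissive, it excludes anyone deteriorating at departure, and it concerns an event called unlikely. Elsewhere the protocol uses 2–3 h for the interval of peak subjective effect (Sections 3.2 and 3.4.4), which spans both scheduled sets. The natural reading is therefore that both must be done, which makes 40% rather than 60% the fair headline. Share of the window is not share of the risk: Section 5.4.4 specifies continuous monitoring for the first 120 minutes only, so later observation is less intensive even for completers. The call also asks about adverse events and persisting sedation, with a second call if needed (Section 5.5). The model draws on all earlier cohorts, and the Dose Setting Committee can overrule it.

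All of this stands, and it limits the size of the problem. It does not remove it: the remaining hours are still scored as observed, and most DLT criteria cannot be recovered by telephone.

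A reader might infer that an early leaver goes home before either drug has peaked. The documents do not support that as a general statement. For baclofen it depends on which of two conflicting peak times applies, and Section 5.4.7 treats 120 min as already past the expected peak effect. For methadone it is marginal after 180 min, and Section 5.4.2 says these long-term users are at steady state.

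**Conclusion.** The point holds as a defect in how partial follow-up is scored, and it does not depend on which baclofen peak time applies. Under the more natural reading, 40% of the window, 2 of 5 NEWS2/GCS sets and 1 of 2 ECGs are missing; under the looser one, 60%, 3 of 5 and 1 of 2.

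Peak exposure after departure is possible but uncertain. The 2–4 h and 88–102 min figures need reconciling, and nothing here says which is right.

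The average bias is probably small: on the assumed ranges, a 25% risk is recorded as 22.5–24.9%. The documents give no frequency of early departure. Section 6.2 expects about 20% drop-out before or at the session without separating the two. It would go too far to infer that the escalation decisions are unsafe or the final dose recommendation invalid. What can be said is that the error runs in one direction only and has most leverage in a single small cohort. The detailed SAP mentioned in Sections 8.3.2 and 8.3.7 may address partial follow-up, but it is not part of these documents.

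**What to change.** Change the rules for model input in Section 3.4.7 and carry them into the detailed SAP:

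- An observed DLT always counts, whenever the participant leaves.
- Replace the 2–3 h wording with a named scheduled set. Require completion of the 180 min set before an early leaver can be scored as no DLT. Otherwise treat that person as not DLT-evaluable and replace them under the provision already in Section 3.4.7. Section 5.8.1 is not a direct substitute: for a participant already dosed it first repeats the study day.
- Flag every early leaver to the Dose Setting Committee.
- At each affected update and at the final analysis, re-run the model without DLT-free early leavers. Report whether the recommended dose or a stopping decision (25% or 92.5% rule) changes. This is needed because 40% of the window is still missing after the 180 min set.
- Reconcile the baclofen peak times in Sections 3.4.5, 5.4.3 and 5.7.1.

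If partial weighting is preferred, the weights should follow the expected timing of DLT onset. Weighting by elapsed time alone assumes uniform onset over 5 hours, which sits badly with the protocol's own expectation of a peak.

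The cost is a few sentences and an extra model run when an early departure occurs. An occasional participant contributes less information or is replaced. Excluding DLT-free leavers errs slightly toward over-estimating risk, so that run is best reported beside the main one rather than in its place.

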## **4 STUDY DESIGN**

### **4.1 Description of Overall Study Design**

This will be a single-blind, adaptive, randomised, placebo-controlled ascending dose study of a single dose of baclofen in opiate-dependent individuals stably maintained on methadone. Participants will be randomised in a 3:1 ratio to baclofen or placebo. Participants allocated to baclofen will be dosed in groups of up to 3, with a maximum available sample size of 64 (up to 48 on baclofen and 16 on placebo). An adaptive model will inform the dosage of baclofen for each patient group based on the trial data accumulated to date.

The primary objective is determination of the maximum safe dose of baclofen at which 15-25% of evaluable participants experience a dose limiting toxicity (DLT, defined in section 3.4.2) for prescribed doses of methadone.

Potentially eligible participants will be identified by telephone screening and invited to attend a screening visit at one of the study sites. Following informed consent, this visit will ascertain study eligibility, medical, psychiatric and dependence history, obtain self-report and rater-report questionnaire measures and administer an actiwatch, to be worn until the morning after the experimental visit.

Eligible participants will be enrolled into the study and randomised to receive baclofen or placebo in a 3:1 ratio. The baclofen dose allocation recommendation (10, 30, 60 or 90mg) will be made by the Bayesian adaptive algorithm, based on the participant's prescribed methadone dose level and previous learning accumulated by the adaptive model. The Dose setting committee (DSC) retains the ability to override the algorithm's dose recommendation if clinically indicated.

Following randomisation, participants will attend the Imperial Clinical Research Facility (ICRF) for a single experimental visit, during which they will consume their usual daily dose of methadone under observation soon after arrival, followed by an acute oral dose of baclofen or placebo approximately 1 hour later, as determined by the adaptive trial algorithm.

Measures of respiratory, cardiovascular, subjective and PK will be obtained periodically for up to 5 hours after baclofen dose.

The following day, participants will receive a follow-up phone call to check welfare and will be required to return their actiwatch via pre-paid envelope, or to their local addiction service, as appropriate.

[figure not shown]
## **4.2 Study visits**

All eligible participants will have:

- Pre-screening assessment by telephone or in their usual clinical addiction service, as appropriate
- One in-person clinical screening visit.
- Randomisation/enrolment
- One in-person experimental study visit
- One follow-up phone-call following the experimental study visit to check for adverse events.

## 4.3 Study design schematics

### 4.3.1 Study procedure schematic

**Key:** **SPO2**; Blood Oxygen Saturation, **ETCO2**; End Tidal Carbon Dioxide, **RR**; Respiration Rate, **ECG**; Electrocardiogram, **COWS**; Clinical Opiate Withdrawal Scale, **Plasma**; Blood Sample, **GCS**; Glasgow Coma Scale, **NEWS2**; National Early Warning Score 2, **BP**; Blood Pressure, **BT**; Body Temperature, **HR**; Heart Rate, **SHAS**; Subjective high assessment scale, **DEQ**; Drug Evaluation, Questionnaire, **VAS**; Visual Analogue Scale, **LSEQ**; Leeds Sleep Evaluation Questionnaire.

### 4.3.2 Experimental Visit Schematic

Experimental study day duration will be approximately 6-7 hours. Start times will be determined according to participant's preference but a typical study day would look like this:

	Procedure	Timepoint (mins)							
	#Baseline	15	30	60	90	120	180	240	300
NEWS2	x	-	-	x	-	x	x	x	x
SpO 2	x	x*	x*	x	x*	x	x	x	x
RR	x	x*	x*	x	x*	x	x	x	x
BP	x	-	-	x	-	x	x	x	x
HR	x	-	-	x	-	x	x	x	x
Body Temp	x	-	-	x	-	x	x	x	x
LOC	x	-	-	x	-	x	x	x	x
GCS	x	-	-	x	-	x	x	x	x
ECG	x	-	-	-	-	x	-	-	x
CO 2	x	x	x	x	x	x	x	x	x
SHAS	x	-	-	x	-	x	x	x	x
DEQ	x	-	-	x	-	x	x	x	x
VAS	x	-	-	x	-	x	x	x	x
Blood Plasma	x	-	-	x	-	x	x	-	x
COWS	x	-	-	-	-	x	-	-	x

#Baseline refers to measurements obtained prior to Time 0, which represents the time at which baclofen/placebo is administered. Shaded area are measures comprising the NEWS2 score. \*At these time points SpO2 and RR measures will be taken in addition to those associated with the NEWS2.

[figure not shown]
### 4.4 Treatment algorithm

A Bayesian dose-escalation adaptive model will be used to determine the baclofen dose allocation and will be informed by the occurrence of dose-limiting toxicity (DLT) events at increasing doses of baclofen (10, 30, 60, 90mg). Participants will be randomised (single-blind) to baclofen or placebo in a 3:1 ratio. If allocated to baclofen, the adaptive model will recommend the dose level for a given patient according to their prescribed dose of methadone and prior information regarding the incidence of DLTs. The model will be updated after each group of up to 3 participants, according to the observed patients' responses. The Dose setting committee (DSC) retains the ability to override the algorithms dose recommendation if clinically indicated.

The study can therefore be stopped earlier for safety if the model suggests that 30mg of baclofen and 60mg of methadone is highly likely to be *unsafe*. The study can also stop

earlier if the highest dose of baclofen (90mg) is highly likely to be *safe*, i.e. below the target toxicity with 120mg of methadone, provided that the study has also achieved sufficient data to meet secondary endpoints.

#### 4.4.1 Schematic for baclofen dose algorithm

Please see section 4.4.2 for definitions of  $p(\text{DLT})$ ,  $p(\text{safe})$ ,  $p(\text{target})$

#### 4.4.2 Baclofen dose decisions

The lowest dose of baclofen (10mg) will be allocated to the first group of 3 participants assigned to receive baclofen. The dose-toxicity model will be continuously updated after each group of at most 3 participants, to recommend dosing for the subsequent group of participants. The model will describe the probability of a patient experiencing a DLT;  $p(\text{DLT})$ , at a given methadone-baclofen dose, the probability of the given dose being safe;  $p(\text{safe})$ , and the probability of the dose being within the target toxicity interval;  $p(\text{target})$ .

The model will establish the combination-toxicity relationship which borrows information between different doses across both drugs, leading to an efficient use of data. The model will output the dosing function that provides the safe dose of baclofen that is most likely to be associated with 15-25% DLT risk for a given dose of methadone.

According to the model, if any of these DLTs are met, then the next group of patients will be assigned to the current (or lower) dose of baclofen, without dose escalation,

depending on the prescribed dose of methadone for the next individual that enters the study.

If there is no DLT, a dose escalation may be advised by the model, again, depending on the prescribed dose of methadone for the next individual that enters the study.

The model will recommend to stop the trial earlier due to safety concerns if the probability that the risk of DLT for 60mg of methadone in combination with 30mg of baclofen exceeds the target range is 25% or more. The model will recommend to stop the trial earlier due to all doses of baclofen being safe if the probability that the risk of DLT for 120mg of methadone in combination with 90mg of baclofen does not exceed the target range is 92.5% or more, representing the 'all-safe-stop criteria'.

The Dose Setting Committee (DSC, comprised of a statistician, clinician and member of the research team) can decide to over-ride any recommendation made by the model, if clinically indicated. Outside of the model parameters, clinical judgement will determine whether responses to baclofen are sufficiently concerning to cease escalation, escalate to a lower dose than planned by the model, or to reduce the average methadone dose for each dose of baclofen examined. If doses of 90mg baclofen are deemed safe by the model with up to and including 120mg methadone, further escalation will cease provided that the data required for secondary endpoints are met.

Should the study team witness multiple DLTs, using their clinical experience they can halt the trial early over safety concerns.

In the scenario that there is a very high probability that all doses are safe before reaching the maximum recruitment of n=48 receiving baclofen, the study will retain the ability to override the all-safe-stop criteria to continue recruitment until we have tested a sufficient range of doses of methadone to ensure we have covered the clinical range of potential methadone doses and/or to explore baclofen dose separation to achieve maximum precision on secondary outcomes.

Given no safety concerns, we expect the *minimum* numbers of participants at each of the doses to be as follows: n=3 @ 10mg baclofen, n=3 @ 30mg baclofen, n=12 @ 60mg baclofen and n=12 @ 90mg baclofen, with n=10 receiving placebo, providing sufficient data to allow adequate exploration of dose separation on primary and secondary outcomes across a range of methadone dose levels, and an assessment of GABA-B receptor sensitivity and any gender effects. These numbers might be exceeded if the variability in response is larger than anticipated, female representation is lower than we would like, or we have not yet been able to test the full range of methadone doses. If a particular baclofen dose is deemed unsafe, then the lower doses would be similarly explored.

## 5 STUDY PROCEDURES

### 5.1 Pre-Screening Procedures

Pre-screening appointments will take place via telephone or within the local addiction services as appropriate, to ensure that participants are likely to be interested, and eligible according to DSM-5 and study criteria. This will take approximately 20 minutes.

